2.3. Exploratory objectives

- To evaluate potential biomarkers in blood or tumor tissue which might predict response to DCC-2618 (ripretinib, ZL-2307)
 - To understand potential drug resistance mechanism to DCC-2618 (ripretinib, ZL-2307) in GIST.
 - To characterize KIT and PDGFRA mutations at baseline and DCC-2618 (ripretinib, ZL-2307)-driven longitudinal mutant allele frequency changes in plasma.

Note: Blood samples and tumor tissues for exploratory purpose will be collected after obtaining the approval of China Human Genetic Resources Administration Office.

3. Study Design

3.1. Overview of Study Design

This is a randomized, open-label, multicenter phase 2 clinical study to compare the efficacy and safety of DCC-2618 (ripretinib, ZL-2307) to sunitinib in GIST patients who progressed on or were intolerant to first-line anticancer treatment with imatinib.

Approximately 98 patients will be randomized in a 1:1 ratio to DCC-2618 (ripretinib, ZL-2307) 150 mg QD by continuous administration or sunitinib 50 mg QD, 4 weeks on, 2 weeks off. Up to 10% of randomized patients may have KIT/PDGFRA WT GIST (wild-type KIT and wild-type PDGFRA regardless of the mutational status of any other gene).

Randomization will be stratified by:

• KIT exon 11 mutation; KIT exon 9 mutation; other (KIT/PDGFRA WT or other KIT [lacking exon 9 or 11]/PDGFRA mutation);

The primary endpoint of the study will be evaluated using the modified Response Evaluation Criteria in Solid Tumors (RECIST) Version 1.1-GIST-specific based on independent radiologic review.

Upon disease progression by RECIST-GIST-specific based on independent radiologic review, patients will discontinue their assigned treatment.

If the investigator doesn't hope to confirm by the independent radiologic review or hopes to terminate the patient's treatment according to progressive disease based on "RECIST v1.1-GIST-specific Criteria" before obtaining results of the independent radiologic review, it is necessary to discuss with the sponsor.

3.2. Number of patients

Approximately 98 patients will be randomized in a 1:1 ratio to receive DCC-2618 (ripretinib, ZL-2307) 150 mg QD by continuous administration or sunitinib 50 mg QD, 4 weeks on, 2 weeks off.

3.3. Study duration

Patients will receive treatment until progressive disease confirmed by the independent radiologic review based on "RECIST v1.1-GIST-specific Criteria", intolerable toxicity or withdrawal of consent.

Patients will discontinue the study drug treatment if patients have progressive disease based on

assessment of the independent radiologic review using "RECIST v1.1-GIST-specific Criteria".

Zai Lab

The longest medication duration of patients is 2 years. For patients with evidence of clinical benefit from the drug and tolerance to the drug and following the study procedure, the treatment duration will be prolonged by reaching an agreement between the sponsor and the investigator.

The study will be terminated when the last patient has progressive disease or 20 months after finishing enrollment or when the sponsor determines to terminate the study, whichever occurs first.

4. Study population

4.1. Inclusion criteria

Eligible patients must meet all the following criteria in order to be included in this clinical trial:

- 1. Male or female patients \geq 18 years of age.
- 2. Histological diagnosis of advanced GIST and capability of providing tumor tissue sample (the interval between tumor tissue collection and signing of informed consent form should be less than 3 years). Otherwise, biopsy is required.
- 3. Provide molecular test report with KIT/PDGFRA mutation status prior to randomization. Mutation status must be identified by tissue-based PCR or sequencing analysis. If molecular test report is unusable or insufficient, an archived tumor tissue sample or fresh live tissue should be tested to confirm mutation status prior to randomization.
- 4. Patients must have progressed on imatinib or have documented intolerance to imatinib. Subjects must have discontinued imatinib treatment 10 days prior to the first dose of the study drug. All prior imatinib treatments will be considered as first-line (such as imatinib adjuvant therapy and imatinib dose increase).
- 5. ECOG PS of 0-2.
- 6. Female patients of childbearing potential must have a negative serum beta-human chorionic gonadotropin (β-hCG) pregnancy test at screening.
- 7. Subjects of reproductive potential should adopt effective contraceptive measures.
- 8. At least 1 measurable lesion according to the "RECIST v1.1-GIST-specific Criteria" (non-nodal lesions must be ≥1.0 cm in the long axis or ≥ double the slide thickness in the long axis); obtaining radiographic image results within 28 days prior to the first dose of study drug.
- 9. Good organ function and bone marrow reserve function, including:
 - Neutrophil count (ANC) $\geq 1,000/\mu L$
 - Hemoglobin $\geq 8 \text{ g/dL}$
 - Platelet count $\geq 75,000 / \mu L$

Total bilirubin $\leq 1.5 \times$ the upper limit of normal (ULN)

Zai Lab

- AST and ALT $\leq 3 \times \text{ULN}$, and AST and ALT $\leq 5 \times \text{ULN}$ in the presence of hepatic metastases
- Creatinine clearance \geq 50 mL/min (based on Cockcroft-Gault Formulas for calculation)
 - Note: Patients should receive no corrective treatment with granular colony stimulating factor or interleukin-11, infusion of red blood cells or platelets or other blood products within 2 weeks prior to detecting haematology.
- Prothrombin time (PT), international normalized ratio (INR) or partial thromboplastin time $\leq 1.5 \times \text{ULN}$. Patients on a stable, maintenance regimen of anticoagulant therapy for at least 30 days prior to study drug administration may have PT/INR measurements $> 1.5 \times ULN$ if, in the opinion of the investigator, the patient is suitable for the study. An adequate rationale must be provided to the sponsor prior to randomization.
- 10. Resolution of all toxicities from prior therapy to ≤Grade 1 or baseline within 1 week prior to the first dose of study drug, excluding alopecia and \le Grade 3 clinically asymptomatic lipase, amylase, and creatine phosphokinase laboratory abnormalities.
- 11. Patient is capable of understanding and complying with the protocol. Subjects should sign the written informed consent before any study-related procedures were performed.

4.2. **Exclusion criteria**

Patients who meet any of the following criteria will be excluded from the study:

- 1. Treatment with any other line of therapy in addition to imatinib for advanced GIST. Imatinibcontaining combination therapy in the first-line treatment should not be enrolled.
- 2. Patients with a prior or concurrent malignancy whose natural history or treatment have the potential to interfere with the safety or efficacy assessment of this clinical trial are not eligible. For example, patients who received adjuvant treatment for cancer and used drugs which have potential activity to GIST or are prohibited by study protocol are not eligible.
- 3. Patient has known active central nervous system metastases.
- 4. New York Heart Association class II IV heart disease, myocardial infarct, active ischemia or any other uncontrolled cardiac condition within the first 6 months of the first dose of study drug such as angina pectoris, clinically significant cardiac arrhythmia requiring therapy, uncontrolled hypertension or congestive heart failure.
- 5. Left ventricular ejection fraction (LVEF) < 50%.
- 6. Arterial thrombotic or embolic events such as cerebrovascular accident (including ischemic attacks) or hemoptysis within the first 6 months of the first dose of study drug.

- 7. Venous thrombotic events (e.g. deep vein thrombosis) or pulmonary arterial events (e.g. pulmonary embolism) within 1 month before the first dose of study drug. Patients on stable anticoagulation therapy for at least one month are eligible.
- 8. 12-lead ECG demonstrating QT interval (QTc) corrected by Fridericia's formula >450 ms in males or > 470 ms in females at screening or history of long QT interval syndrome.
- 9. Use of moderate or strong inhibitors and/or inducers of cytochrome P450 (CYP) 3A4 within 14 days or 5 x the half-life (whichever is longer) prior to the first dose of study drug, including certain herbal medications (eg, St. John's Wort) and consumption of grapefruit or grapefruit juice within 14 days prior to the first dose of study drug. For CYP3A4 enzyme inhibition/induction-related drugs, please refer to the website of the Indiana University, School of Medicine (http://medicine.iupui.edu/clinpharm/ddis/main-table/).
- 10. Use of known substrates or inhibitors of breast cancer resistance protein (BCRP) transporters within 14 days or 5 x the half-life (whichever is longer) prior to the first dose of study drug. For information of inhibitors and substrates, please refer to Food and Drug Administration (FDA) website:

 https://www.fda.gov/Drugs/DevelopmentApprovalProcess/DevelopmentResources/DrugInt eractionsLabeling/ucm093664.htm.
- 11. Major surgeries (e.g. Abdominal laparotomy) within 4 weeks of the first dose of study drug; all major surgical wounds must be healed and free of infection or dehiscence before the first dose of study drug.
- 12. Any other clinically significant comorbidities, such as uncontrolled pulmonary disease, active infection, or any other condition, which in the judgment of the investigator, could compromise compliance with the protocol, interfere with interpretation of the study results, or predispose the patient to safety risks.
- 13. Known human immunodeficiency virus or hepatitis C infection only if the patient is taking medications that are excluded per protocol, hepatitis B virus (HBV) DNA > 2000 IU/ml or > 10⁴ copies/ml.
- 14. Female patients who are pregnant or lactating or who plan to become pregnant during the study treatment period.
- 15. Known hypersensitivity to any component of the study drug. Patients with Stevenson Johnson syndrome in previous TKI treatment need to be excluded.
- 16. Gastrointestinal abnormalities including but not limited to:
 - inability to take oral medication
 - malabsorption syndrome
 - Requiring intravenous (IV) nutrition

17. Any active hemorrhages, excluding hemorrhoids or gum bleeding.

5. Administration and Management of Study drugs

5.1. Sunitinib

5.1.1. Sunitinib Description

Sunitinib will be provided as scored hard capsules and contain sunitinib malate equivalent to 12.5 mg of sunitinib. In active ingredients include mannitol, croscarmellose sodium, povidone (K-25) and magnesium stearate.

5.2. DCC-2618 (Ripretinib, ZL-2307)

5.2.1. Description of DCC-2618 (ripretinib, ZL-2307)

DCC-2618 (ripretinib, ZL-2307) is a 50 mg oral tablet. The tablet contain active ingredient. Its formulation is amorphous dispersion and cellulose acetate succinate (mass ratio of grade H polymer matrix [33.33%] is 25% [w/w]). Other excipients include microcrystalline cellulose (Avicel PH-101) (29.84%), lactose 310 (29.83%), crosslinked polyvinylpyrrolidone (5%), fumed silica (CabOSil M5P or Syloid 244FP) (1%) and magnesium stearate (1%).

5.3. Dosage and route of administration of study drugs

The study drug can be distributed only under the supervision of the investigator or authorized designated personnel and administered to subjects of the study only. Patients will be randomized to receive DCC-2618 (ripretinib, ZL-2307) 150 mg QD by continuous administration based on a 42-day cycle, or sunitinib 50 mg QD in 6 weeks (42 days) with 4 weeks continuous dosing followed by 2 weeks break. According to the approved package insert, dose adjustment of sunitinib is allowed.

The investigator or designated personnel must guide patients to take DCC-2618 (ripretinib, ZL-2307) according to the following method:

- It should be taken at the same time each day.
- Patient should take study srug with or without food.
- Swallow as a whole. Tablets must not be crushed, chewed or dissolved in liquid or food.
- Administration date, dose and time of DCC-2618 (ripretinib, ZL-2307) should be recorded 3 days before and on the day of PK sampling.

If the patient forgets to take DCC-2618 (ripretinib, ZL-2307) at the predetermined time, the patient can take the predetermined dose within 8 hours upon the predetermined time. If it has been over 8 hours from the predetermined time, the missing dose must be ignored and the next predetermined dose of drug can be taken to continue the treatment.

Please refer to the approved package insert for description of administration of sunitinib.

On the scheduled study visit date, patients will be informed of taking the study drug at study site according to Table 1 (Schedule of Assessments). Administration of the study drug must be carried out at study site after finishing pre-dose assessment. Administration date, dose and time of the study drug must be recorded in source documents of patients.

If subjects vomit immediately after taking the study drug, the dose should not be "supplemented" and prophylactic antemetics can be used before the next dose.

Please refer to Section 7.12 and the approved package insert of sunitinib for information of overdose.

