Dosage: 50 mg QD, in 6 weeks (42 days) with 4 weeks continuous dosing followed by 2 weeks break. Dose modifications are allowed per approved package insert.

Administration route: oral

Zai Lab

Primary endpoints:

Progression-free survival (PFS):Independent radiologic review will assess PFS according to "RECIST v1.1-GIST-specific Criteria" which include:

- No lymph nodes chosen as target lesions; enlarged lymph nodes will be followed as non-target lesions.
- No bone lesions chosen as target lesions;
- Positron emission tomography (PET) not acceptable for radiological evaluation;
- A progressively growing new tumor nodule within a pre-existing tumor mass must meet the following criteria to be considered as unequivocal evidence of progression according to the modification of RECIST Version 1.1: (a) the lesion is at least 2 cm in size and definitively a new active GIST lesion (e.g. enhancing with contrast or other criteria to rule out artefact); or (b) the lesion has to be

expanding on at least 2 sequential imaging studies.

Secondary endpoints:

Efficacy Endpoints

- ORR (confirmed CR + confirmed PR) based on independent radiologic
- Disease control rate (DCR) at months 6, 9 and 12, assessed by independent radiologic review
- PFS assessed by the investigator according to "RECIST v1.1-GISTspecific Criteria"
- Overall survival (OS)

Safety:

- Incidence of treatment emergent adverse event (TEAE), adverse event of special interest (AESI) and serious adverse event (SAE); severity of adverse event will be assessed (based on NCI CTCAE 5.0);
- Incidence of adverse events resulting in dose adjustment of the study drug or termination of the study;
- Changes in each parameter like ECOG score, vital signs, electrocardiogram, left ventricular ejection fraction, dermatologic examination and laboratory indicators from baseline.

Pharmacokinetic profiles:

Descriptive statistics and summary of drug concentration at relevant time points will be carried out according to plasma concentration of DCC-2618 (ripretinib, ZL-2307) after administration. If necessary, pharmacokinetic data of this study will be included into population PK analysis with industrial standard software. Population PK report will be drafted independently and not taken as the appendix of the study report.

Exploratory endpoint:

KIT/PDGFRA mutation of tumor tissues at baseline and specific time

Study Endpoints

points (e.g., resection of metastasis or progressive disease during the study).

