In population with KIT exon 11 mutation, it was assumed in the foreign study that mPFS of the test group was 9 months and mPFS of the control group was 5 months, and HR of the test group to the control group was 0.556. If the study keeps $\geq 50\%$ of the overall effect size of study INTRIGUE in population with KIT exon 11 mutation, that is, point estimate of HR should be ≤ 0.778 , it will be considered that results based on KIT exon 11 mutation population in this study are consistent with those in study INTRIGUE. If 26 PFS events occur in population with KIT exon 11 mutation, the conclusion of consistence with study INTRIGUE can be drawn with a probability of 80%.

Note: If a patient has exon 11 mutation along with 1) exon 9 and/or PDGFRA mutation, the patient will be considered with exon 11 mutation at randomization. Mutation type of the patient will be defined according to a mutation with a higher MAF if the patient has mutation allele frequency (MAF) data; 2) other KIT exon mutation, the patient will be considered with exon 11 mutation at randomization.

Study duration

Patients will receive treatment until progressive disease confirmed by the independent radiologic review based on "RECIST v1.1-GIST-specific Criteria", intolerable toxicity or withdrawal of consent.

Patients will discontinue the study drug treatment if patients have progressive disease based on assessment of the independent radiologic review using

	"RECIST v1.1-GIST-specific Criteria".
	The longest medication duration of patients is 2 years. For patients with evidence of clinical benefit from the drug and tolerance to the drug and following the study procedure, the treatment duration will be prolonged by reaching an agreement between the sponsor and the investigator.
	The study will be terminated when the last patient has progressive disease or 20 months after finishing enrollment or when the sponsor determines to terminate the study, whichever occurs first.
Schedule of visits and the content thereof	Please refer to Table 1

Zai Lab

Figure 1: Schematic diagram of the study

Patients are histologically diagnosed with GIST and must have progressed during receiving imatinib treatment or intolerance.

OS DCC 2618 N = 49150 mg A treatment cycle consists of QD Screening and consecutive 42 days of dosing Safety **PFS** Random follow-up assignment Sunitinib N = 4950 mg QD 4W on/2W off 4W on/2W off, 42 days for a treatment cycle.

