Patients will receive treatment until progressive disease based on "RECIST v1.1-GIST-specific Criteria", intolerable adverse events or withdrawal of consent. If progressive disease is confirmed by the independent radiologic review using "RECIST v1.1-GIST-specific Criteria", patients who receive DCC-2618 or sunitinib will discontinue treatment with the study drug.

Table 1: Schedule of Assessments

Evaluation/Procedure ¹	Screening 2		Cycle 1		Сус	le 2	≥ Cycle 3	EOT visit	Safety follow- up	Overall survival
Cycle Day	-28 to -1	1 (Baseline)	15 (± 1 day)	29 (± 1 day)	1 (± 3 day)	29 (± 3 day)	1 (± 3 day)	(Within 7 days after the last dose)	Within 30 days after the last dose (± 5 day)	follow-up ³ (Every 2 month \pm 10 days)
Come to the Study Site	X	X	X	X	X	X	X	X		
Tel									X	X
Informed consent	X									
Inclusion/Exclusion criteria	X									
Previous medical history and tumor history	X									
Previous medications/treatment ⁴	X									
Pregnancy test ⁵	X	X*			X		X	X		
Hepatitis B/C tests ⁶	X						X	X		
HIV antibody test	X									
Clinical laboratory tests										
Blood routine	X	X*	X	X	X	X	X	X		
Blood biochemistry	X	X*	X	X	X	X	X	X		
Blood coagulation function ⁷	X	X*	X	X	X	X	X	X		
Urine routine ⁸	X	X*			X		X	X		
TSH, FT3 and FT4 ⁹	X	X*					X	X		
Physical examination	X	Examination will be arranged based on clinical findings and/or patients' chief complaints								
ECOG PS ¹⁰	X	X*	X	X	X	X	X	X		
Vital signs and weight ¹¹	X	X*	X	X	X	X	X	X		
Height	X									
12-lead ECG ¹²	X	X*			X		X	X		
Echocardiography/13	X						X	X		
Dermatologic examination ¹⁴	X						X	X		

Evaluation/Procedure ¹	Screening 2		Cycle 1		Cyc	le 2	≥ Cycle 3	EOT visit	Safety follow- up	Overall survival
Cycle Day	-28 to -1	1 (Baseline)	15 (± 1 day)	29 (± 1 day)	1 (± 3 day)	29 (± 3 day)	1 (± 3 day)	(Within 7 days after the last dose)	Within 30 days after the last dose (± 5 day)	follow-up³ (Every 2 month ± 10 days)
AEs reporting			Co	ntinuing from	m signing an l	CF to the saf	fety follow-up			
Concomitant medicines/other treatment				From t	he first dose o	f the study d	rug to safety follo	ow-up		
Administration of study drug ¹⁵		X	X	X	X	X	X			
Distribution and reconciliation of the study drug		X			X		X			
PK sampling ¹⁶		X	X		X		X			
Molecular test report, marking KIT/PDGFRA mutation status ¹⁷	X									
Archived tumor tissue sample/tumor biopsy ¹⁸	X									
Optional tumor biopsy 19								X		
Imageological examination ²⁰	X				X		X			
PD sampling (plasma) ²¹		X						X		

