- ^{14.} For all patients, skin lesions will be assessed by a consultant dermatologist within 28 days (baseline) prior to C1D1, especially squamous cell carcinoma of skin, actinic keratosis and keratoacanthoma. After that, patients will receive assessment on C3D1, and Day 1 of every subsequent 3 cycles (that is, Cycles 6, 9 and 12, etc.), at EOT visit and when clinically necessary. Dermatologic examination meeting standard of the study protocol performed prior to informed consent can be used for screening evaluation as long as the examination is performed within 28 days prior to the first dose of the study drug. Dermatological examinations during the treatment period may be performed within at most 7 days before the corresponding follow-up visit or after the administration on the date of the follow-up visit. Please refer to Section 6.11.6 for further information.
- 15. On the date of study visit after finishing pre-dose evaluation, patients will be told to take the study drug at study site. Please refer to Section 5.3 for detailed information of dose and administration.
- Only patients who use DCC-2618 (ripretinib, ZL-2307) will receive PK sampling at the following time points: before administration and 6 hours after administration on C1D1, before administration, 2 and 6 hours after administration on C1D15, and before administration on C2D1 and C3D1. All pre-dose samples must be collected within 60 minutes prior to administration and all post-dose samples must be collected within the specified time point ± 30 minutes. If the sponsor requires, unscheduled PK samples can be collected when new, suspicious, and treatment-related adverse events occur.
- Molecular test report with KIT/PDGFRA mutation status must be provided. Mutation status must be identified by tissue-based PCR or sequencing analysis. Molecular test report with KIT/PDGFRA mutation status must be provided to the investigator before randomization so that the investigator can confirm randomization stratification factor. If molecular test report is not available or insufficient, biopsy of an archival tumor tissue sample or fresh tumor tissue is required for mutation status confirmation by the central laboratory prior to randomization.

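### Table 1, its note 15 and section 5.3 direct on-site study drug intake at the Day 29 visits in both arms, but Day 29 is the first day of the sunitinib break

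*Combined protocol and SAP*

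**What the plan says.** **Regimen.** The synopsis gives the sunitinib dosage as "50 mg QD, in 6 weeks (42 days) with 4 weeks continuous dosing followed by 2 weeks break". Section 5.3 repeats it ("sunitinib 50 mg QD in 6 weeks (42 days) with 4 weeks continuous dosing followed by 2 weeks break"), and Figure 1 shows the same cycle ("4W on/2W off, 42 days for a treatment cycle").

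**Schedule.** In Table 1 the row "Administration of study drug" has an X in all six on-treatment columns: C1D1, C1D15, C1D29, C2D1, C2D29 and Day 1 of Cycle 3 onward. The row is not split by arm.

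**Instruction behind the X.** Note 15 to Table 1 reads: "On the date of study visit after finishing pre-dose evaluation, patients will be told to take the study drug at study site". It then sends the reader to section 5.3 for dose and administration. Section 5.3 says: "On the scheduled study visit date, patients will be informed of taking the study drug at study site according to Table 1". It adds: "Administration of the study drug must be carried out at study site after finishing pre-dose assessment". All three sentences use the generic term for study drug, which covers both arms.

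**Exemption.** None is stated for sunitinib at Day 29. For sunitinib, beyond the regimen itself, section 5.3 only refers to the package insert for administration, dose adjustment and overdose.

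**The concern.** A site with a sunitinib patient at a Day 29 visit has two written instructions that cannot both be met. If the patient takes a dose at the visit, the stated control regimen is not followed. If the patient does not, a marked Table 1 item is left undone.

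Other rules depend on which instruction governs. Section 5.7 assesses compliance by drug counts, section 10.2 has sites record all protocol deviations, and section 7.12 defines overdose and medication error. None of them says how to classify a break-day dose, or a Day 29 administration box left empty. Section 5.4 also counts the 2-week withdrawal toward its 28-day interruption limit, so a dose taken inside the break would disturb that count. The ambiguity exists only in the control arm of an open-label, multicenter trial.

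The protocol does make items arm-specific elsewhere. Note 16, for example, restricts PK sampling: "Only patients who use DCC-2618 (ripretinib, ZL-2307) will receive PK sampling at the following time points". Note 15 carries no such restriction.

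**Working it through.** The plan states no figure to reproduce here. The check is a day count and a comparison of passages.

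**Inputs**
- Sunitinib: 4 weeks on, 2 weeks off, 42-day cycle (synopsis, Figure 1, section 5.3).
- C1D29 visit window: ±1 day. C2D29 visit window: ±3 days (Table 1 header).
- Administration row: six X marks across six on-treatment columns (Table 1).

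**Step 1: dosing and break days.** 4 × 7 = 28 dosing days and 2 × 7 = 14 break days. 28 + 14 = 42, which agrees with the stated cycle. Dosing days are 1-28 and break days are 29-42, so nominal Day 29 is break day 1.

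**Step 2: is the X at Day 29 a table-reading artefact?** The row has exactly as many marks as there are on-treatment columns. In the same table the PK row is blank at both Day 29 columns, which matches the time points in note 16 (C1D1, C1D15, C2D1, C3D1). The columns are therefore aligned and the Day 29 marks are real.

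**Step 3: visit windows against the break.**

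| Visit | Permitted days | Dosing days | Break days | Share in break |
|---|---|---|---|---|
| C1D29 ±1 | 28-30 | 28 | 29-30 | 2 of 3 |
| C2D29 ±3 | 26-32 | 26-28 | 29-32 | 4 of 7 |

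These are shares of calendar days, not probabilities, because the plan does not say how visits spread over the window.

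**Step 4: other visits.** Day 1 and Day 15 fall in the dosing period. From Cycle 3 only Day 1 visits are scheduled. The conflict is confined to C1D29 and C2D29, so at most two visits per sunitinib patient.

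**Assumption.** Each sunitinib course starts on Day 1 of its cycle. If a site started the second course on the actual date of a C2D1 visit, which has its own ±3-day window, the last dosing day would lie between Day 25 (28 − 3) and Day 31 (28 + 3). The overlap would shift but would not disappear.

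**The case against.** The strongest reply is that the text, read as a whole, does not create a dose on a non-dosing day.

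- Note 15 points to section 5.3, which itself states the break and refers sunitinib administration to the package insert. The on-site sentence in 5.3 can be read as fixing the place and order of a dose that is due.
- Section 5.4 has visits continue under Table 1 while dosing is interrupted, in both arms. If every X compelled a dose, a patient on a toxicity hold would have to dose at each visit, which cannot be meant. The same section mentions the 2-week withdrawal, so its authors had the off period in view.
- The distribution row of Table 1 has no X at either Day 29 visit. A dose then would have to come from drug dispensed earlier, and the quantity dispensed is not stated.
- The regimen appears in the synopsis, Figure 1 and sections 3.1, 3.2 and 5.3. Against it stands one generic table row with its note.

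This makes literal dosing on break days unlikely. It does not remove the conflict: section 5.4 does not name the Day 29 visits, and no passage withdraws the X marks or limits note 15 to one arm.

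A reader might also infer something larger: 49 × 2 = 98 sunitinib doses in the break, each 1/28 = 3.6% of a cycle's dosing days, with sites dividing on the rule and control-arm exposure changed. The documents do not support that. The figure of 98 needs all 49 patients still on treatment at C2D29, every visit held on Day 29 or later, and every site setting the regimen aside. Nothing in the documents predicts how sites would divide.

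**Conclusion.** The inconsistency is in the current text and the day count is certain. Table 1, note 15 and the on-site rule in section 5.3 conflict with the stated sunitinib schedule at C1D29 (when held on Days 29-30) and C2D29 (when held on Days 29-32), and at no other visit. On Day 28 in Cycle 1 and Days 26-28 in Cycle 2 there is no conflict.

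The size is small. Sites will probably follow the regimen. What remains is a wrong written instruction, spurious or inconsistent deviation and compliance records in the control arm, and at most an occasional break-day dose. The event target, the consistency criterion and the primary PFS analysis are unaffected.

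This rests on sunitinib courses starting on Day 1 of each cycle. The expectation about site behaviour is a judgement from the surrounding text, not a figure in the plan. It is still worth correcting, because the schedule as written would breach the stated control regimen if it were followed.

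**What to change.** Reconcile the Table 1 administration row at C1D29 and C2D29, note 15 and section 5.3 with the stated sunitinib schedule, so that all of them give one instruction for the sunitinib arm at Day 29 visits. The instruction should cover visits that the window moves into or out of the break. State also how the Day 29 administration item is recorded in that arm for compliance and deviation purposes. The sponsor decides which dosing instruction applies; none is proposed here.

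The cost is one footnote to Table 1 and a matching sentence in section 5.3. No visits or procedures are added.
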